# Appendix B

|                                                                |             |               |       |               |               |       |               |               |         |              |              |         |
|----------------------------------------------------------------|-------------|---------------|-------|---------------|---------------|-------|---------------|---------------|---------|--------------|--------------|---------|
| Chronic kidney disease v2; n (%)                               | 80 (5.4%)   | 116 (4.2%)    | 0.06  | 76 (3.1%)     | 102 (2.6%)    | 0.03  | 345 (6.9%)    | 189 (5.5%)    | 0.06    | 501 (5.6%)   | 407 (4.0%)   | 0.07    |
| CKD Stage 3-4; n (%)                                           | 48 (3.3%)   | 90 (3.2%)     | 0.01  | 56 (2.3%)     | 75 (1.9%)     | 0.03  | 249 (5.0%)    | 143 (4.2%)    | 0.04    | 353 (4.0%)   | 308 (3.1%)   | 0.05    |
| Occurrence of hypertensive nephropathy; n (%)                  | 41 (2.8%)   | 51 (1.8%)     | 0.07  | 53 (2.2%)     | 69 (1.8%)     | 0.03  | 213 (4.3%)    | 98 (2.9%)     | 0.08    | 307 (3.4%)   | 218 (2.2%)   | 0.07    |
| Occurrence of miscellaneous renal insufficiency v2; n (%)      | 92 (6.2%)   | 163 (5.9%)    | 0.01  | 132 (5.4%)    | 192 (5.0%)    | 0.02  | 326 (6.5%)    | 229 (6.7%)    | -0.01   | 550 (6.2%)   | 584 (5.8%)   | 0.02    |
| Other Covariates                                        |             |               |       |               |               |       |               |               |         |              |              |         |
| Liver disease; n (%)                                           | ** (0.5%)   | ** (0.1%)     | 0.07  | 0 (0.0%)      | ** (0.1%)     | -0.04 | 28 (0.6%)     | ** (0.2%)     | 0.06    | #VALUE!      | #VALUE!      | #VALUE! |
| Osteoarthritis; n (%)                                          | 283 (19.2%) | 553 (19.9%)   | -0.02 | 397 (16.1%)   | 570 (14.7%)   | 0.04  | 1,164 (23.4%) | 836 (24.5%)   | -0.03   | 1844 (20.7%) | 1959 (19.5%) | 0.03    |
| Other arthritis, arthropathies and musculoskeletal pain; n (%) | 868 (59.0%) | 1,587 (57.0%) | 0.04  | 1,414 (57.4%) | 2,100 (54.2%) | 0.06  | 2,917 (58.5%) | 1,938 (56.9%) | 0.03    | 5199 (58.3%) | 5625 (55.9%) | 0.05    |
| Dorsopathies; n (%)                                            | 440 (29.9%) | 894 (32.1%)   | -0.05 | 634 (25.7%)   | 995 (25.7%)   | 0.00  | 1,702 (34.2%) | 1,139 (33.4%) | 0.02    | 2776 (31.1%) | 3028 (30.1%) | 0.02    |
| Fractures; n (%)                                               | 62 (4.2%)   | 99 (3.6%)     | 0.03  | 78 (3.2%)     | 114 (2.9%)    | 0.02  | 347 (7.0%)    | 227 (6.7%)    | 0.01    | 487 (5.5%)   | 440 (4.4%)   | 0.05    |
| Falls v2; n (%)                                                | 88 (6.0%)   | 140 (5.0%)    | 0.04  | 47 (1.9%)     | 98 (2.5%)     | -0.04 | 241 (4.8%)    | 124 (3.6%)    | 0.06    | 376 (4.2%)   | 362 (3.6%)   | 0.03    |
| Osteoporosis; n (%)                                            | 66 (4.5%)   | 115 (4.1%)    | 0.02  | 53 (2.2%)     | 68 (1.8%)     | 0.03  | 400 (8.0%)    | 306 (9.0%)    | -0.04   | 519 (5.8%)   | 489 (4.9%)   | 0.04    |
| Depression; n (%)                                              | 286 (19.4%) | 455 (16.3%)   | 0.08  | 334 (13.6%)   | 495 (12.8%)   | 0.02  | 1,352 (27.1%) | 888 (26.1%)   | 0.02    | 1972 (22.1%) | 1838 (18.3%) | 0.09    |
| Anxiety; n (%)                                                 | 305 (20.7%) | 617 (22.2%)   | -0.04 | 407 (16.5%)   | 699 (18.0%)   | -0.04 | 1,372 (27.5%) | 959 (28.2%)   | -0.02   | 2084 (23.4%) | 2275 (22.6%) | 0.02    |
| Sleep_Disorder; n (%)                                          | 74 (5.0%)   | 81 (2.9%)     | 0.11  | 196 (8.0%)    | 109 (2.8%)    | 0.23  | 376 (7.5%)    | 105 (3.1%)    | 0.20    | 646 (7.2%)   | 295 (2.9%)   | 0.20    |
| Dementia; n (%)                                                | 73 (5.0%)   | 136 (4.9%)    | 0.00  | 49 (2.0%)     | 70 (1.8%)     | 0.01  | 577 (11.6%)   | 375 (11.0%)   | 0.02    | 699 (7.8%)   | 581 (5.8%)   | 0.08    |
| Delirium; n (%)                                                | 34 (2.3%)   | 80 (2.9%)     | -0.04 | 42 (1.7%)     | 55 (1.4%)     | 0.02  | 345 (6.9%)    | 203 (6.0%)    | 0.04    | 421 (4.7%)   | 338 (3.4%)   | 0.07    |
| Psychosis; n (%)                                               | 25 (1.7%)   | 51 (1.8%)     | -0.01 | 25 (1.0%)     | 37 (1.0%)     | 0.00  | 418 (8.4%)    | 305 (9.0%)    | -0.02   | 468 (5.2%)   | 393 (3.9%)   | 0.06    |
| Obesity; n (%)                                                 | 561 (38.1%) | 974 (35.0%)   | 0.06  | 869 (35.3%)   | 1,303 (33.6%) | 0.04  | 1,465 (29.4%) | 837 (24.6%)   | 0.11    | 2895 (32.5%) | 3114 (30.9%) | 0.03    |
| Overweight; n (%)                                              | 64 (4.3%)   | 193 (6.9%)    | -0.11 | 74 (3.0%)     | 212 (5.5%)    | -0.12 | 175 (3.5%)    | 165 (4.8%)    | -0.07   | 313 (3.5%)   | 570 (5.7%)   | -0.11   |
| Smoking; n (%)                                                 | 538 (36.5%) | 1,004 (36.1%) | 0.01  | 444 (18.0%)   | 742 (19.2%)   | -0.03 | 2,380 (47.8%) | 1,651 (48.5%) | -0.01   | 3362 (37.7%) | 3397 (33.8%) | 0.08    |
| Alcohol abuse or dependence; n (%)                             | 25 (1.7%)   | 56 (2.0%)     | -0.02 | 33 (1.3%)     | 45 (1.2%)     | 0.01  | 102 (2.0%)    | 80 (2.3%)     | -0.02   | 160 (1.8%)   | 181 (1.8%)   | 0.00    |
| Drug abuse or dependence; n (%)                                | 75 (5.1%)   | 163 (5.9%)    | -0.04 | 50 (2.0%)     | 87 (2.2%)     | -0.01 | 319 (6.4%)    | 228 (6.7%)    | -0.01   | 444 (5.0%)   | 478 (4.8%)   | 0.01    |
| COPD; n (%)                                                    | 256 (17.4%) | 430 (15.5%)   | 0.05  | 219 (8.9%)    | 306 (7.9%)    | 0.04  | 1,312 (26.3%) | 902 (26.5%)   | 0.00    | 1787 (20.0%) | 1638 (16.3%) | 0.10    |
| Asthma; n (%)                                                  | 203 (13.8%) | 348 (12.5%)   | 0.04  | 284 (11.5%)   | 441 (11.4%)   | 0.00  | 773 (15.5%)   | 484 (14.2%)   | 0.04    | 1260 (14.1%) | 1273 (12.7%) | 0.04    |
| Obstructive sleep apnea; n (%)                                 | 261 (17.7%) | 405 (14.6%)   | 0.08  | 375 (15.2%)   | 538 (13.9%)   | 0.04  | 748 (15.0%)   | 465 (13.7%)   | 0.04    | 1384 (15.5%) | 1408 (14.0%) | 0.04    |
| Pneumonia; n (%)                                               | 258 (17.5%) | 513 (18.4%)   | -0.02 | 363 (14.7%)   | 651 (16.8%)   | -0.06 | 1,074 (21.6%) | 748 (22.0%)   | -0.01   | 1695 (19.0%) | 1912 (19.0%) | 0.00    |
| Other Medications                                       |             |               |       |               |               |       |               |               |         |              |              |         |
| Use of ACE inhibitors; n (%)                                   | 223 (15.1%) | 334 (12.0%)   | 0.09  | 392 (15.9%)   | 614 (15.8%)   | 0.00  | 751 (15.1%)   | 437 (12.8%)   | 0.07    | 1366 (15.3%) | 1385 (13.8%) | 0.04    |
| Use of ARBs; n (%)                                             | 94 (6.4%)   | 200 (7.2%)    | -0.03 | 218 (8.8%)    | 364 (9.4%)    | -0.02 | 233 (4.7%)    | 163 (4.8%)    | 0.00    | 545 (6.1%)   | 727 (7.2%)   | -0.04   |
| Use of Loop Diuretics - United; n (%)                          | 117 (7.9%)  | 190 (6.8%)    | 0.04  | 166 (6.7%)    | 232 (6.0%)    | 0.03  | 677 (13.6%)   | 383 (11.2%)   | 0.07    | 960 (10.8%)  | 805 (8.0%)   | 0.10    |
| Use of other diuretics-United; n (%)                           | 34 (2.3%)   | 60 (2.2%)     | 0.01  | 52 (2.1%)     | 78 (2.0%)     | 0.01  | 138 (2.8%)    | 74 (2.2%)     | 0.04    | 224 (2.5%)   | 212 (2.1%)   | 0.03    |
| Use of nitrates-United; n (%)                                  | 20 (1.4%)   | 42 (1.5%)     | -0.01 | 33 (1.3%)     | 43 (1.1%)     | 0.02  | 158 (3.2%)    | 123 (3.6%)    | -0.02   | 211 (2.4%)   | 208 (2.1%)   | 0.02    |
| Use of other hypertension drugs; n (%)                         | 33 (2.2%)   | 69 (2.5%)     | -0.02 | 65 (2.6%)     | 89 (2.3%)     | 0.02  | 235 (4.7%)    | 147 (4.3%)    | 0.02    | 333 (3.7%)   | 305 (3.0%)   | 0.04    |
| Use of Anti-arrhythmics; n (%)                                 | 16 (1.1%)   | 34 (1.2%)     | -0.01 | 25 (1.0%)     | 59 (1.5%)     | -0.05 | 57 (1.1%)     | 53 (1.6%)     | -0.04   | 98 (1.1%)    | 146 (1.5%)   | -0.04   |
| Use of COPD/asthma meds- United; n (%)                         | 243 (16.5%) | 463 (16.6%)   | 0.00  | 359 (14.6%)   | 635 (16.4%)   | -0.05 | 1,077 (21.6%) | 815 (23.9%)   | -0.05   | 1679 (18.8%) | 1913 (19.0%) | -0.01   |
| Use of statins; n (%)                                          | 288 (19.6%) | 557 (20.0%)   | -0.01 | 459 (18.6%)   | 739 (19.1%)   | -0.01 | 1,330 (26.7%) | 935 (27.5%)   | -0.02   | 2077 (23.3%) | 2231 (22.2%) | 0.03    |
| Use of other lipid-lowering drugs; n (%)                       | 47 (3.2%)   | 95 (3.4%)     | -0.01 | 94 (3.8%)     | 153 (3.9%)    | -0.01 | 236 (4.7%)    | 155 (4.6%)    | 0.00    | 377 (4.2%)   | 403 (4.0%)   | 0.01    |
| Use of antiplatelet agents; n (%)                              | 24 (1.6%)   | 43 (1.5%)     | 0.01  | 53 (2.2%)     | 92 (2.4%)     | -0.01 | 235 (4.7%)    | 161 (4.7%)    | 0.00    | 312 (3.5%)   | 296 (2.9%)   | 0.03    |
| Use of heparin and other low-molecular weight heparins; n (%)  | 840 (57.1%) | 122 (4.4%)    | 1.39  | ** (0.1%)     | ** (0.0%)     | 0.04  | 2,098 (42.1%) | 154 (4.5%)    | 0.99    | #VALUE!      | #VALUE!      | #VALUE! |
| Use of NSAIDs; n (%)                                           | 156 (10.6%) | 344 (12.4%)   | -0.06 | 348 (14.1%)   | 620 (16.0%)   | -0.05 | 542 (10.9%)   | 385 (11.3%)   | -0.01   | 1046 (11.7%) | 1349 (13.4%) | -0.05   |
| Use of opioids- United; n (%)                                  | 589 (40.0%) | 1,111 (39.9%) | 0.00  | 1,127 (45.7%) | 1,713 (44.2%) | 0.03  | 2,163 (43.4%) | 1,464 (43.0%) | 0.01    | 3879 (43.5%) | 4288 (42.6%) | 0.02    |
| Use of antidepressants; n (%)                                  | 385 (26.2%) | 715 (25.7%)   | 0.01  | 560 (22.7%)   | 915 (23.6%)   | -0.02 | 1,907 (38.3%) | 1,309 (38.4%) | 0.00    | 2852 (32.0%) | 2939 (29.2%) | 0.06    |
| Use of antipsychotics; n (%)                                   | 69 (4.7%)   | 147 (5.3%)    | -0.03 | 94 (3.8%)     | 144 (3.7%)    | 0.01  | 763 (15.3%)   | 544 (16.0%)   | -0.02   | 926 (10.4%)  | 835 (8.3%)   | 0.07    |
| Labs                                                    |             |               |       |               |               |       |               |               |         |              |              |         |
| Lab values- HbA1c (%) v3; n (%)                                | 129 (8.8%)  | 284 (10.2%)   | -0.05 | ** (0.4%)     | 35 (0.9%)     | -0.06 | N/A           | N/A           | #VALUE! | #VALUE!      | 319 (4.8%)   | #VALUE! |
| Lab values- HbA1c (%) (within 3 months) v3; n (%)              | 75 (5.1%)   | 179 (6.4%)    | -0.06 | ** (0.3%)     | 23 (0.6%)     | -0.04 | N/A           | N/A           | #VALUE! | #VALUE!      | 202 (3.0%)   | #VALUE! |
| Lab values- HbA1c (%) (within 6 months) v3; n (%)              | 129 (8.8%)  | 284 (10.2%)   | -0.05 | ** (0.4%)     | 35 (0.9%)     | -0.06 | N/A           | N/A           | #VALUE! | #VALUE!      | 319 (4.8%)   | #VALUE! |
| Lab values- BNP; n (%)                                         | 22 (1.5%)   | 37 (1.3%)     | 0.02  | 0 (0.0%)      | ** (0.2%)     | -0.06 | N/A           | N/A           | #VALUE! | 022 (0.6%)   | #VALUE!      | #VALUE! |
| Lab values- BNP (within 3 months); n (%)                       | 21 (1.4%)   | 35 (1.3%)     | 0.01  | 0 (0.0%)      | ** (0.2%)     | -0.06 | N/A           | N/A           | #VALUE! | 021 (0.5%)   | #VALUE!      | #VALUE! |
| Lab values- BNP (within 6 months); n (%)                       | 22 (1.5%)   | 37 (1.3%)     | 0.02  | 0 (0.0%)      | ** (0.2%)     | -0.06 | N/A           | N/A           | #VALUE! | 022 (0.6%)   | #VALUE!      | #VALUE! |
| Lab values- BUN (mg/dl); n (%)                                 | 290 (19.7%) | 642 (23.1%)   | -0.08 | 18 (0.7%)     | 49 (1.3%)     | -0.06 | N/A           | N/A           | #VALUE! | 308 (7.8%)   | 691 (10.4%)  | -0.09   |
| Lab values- BUN (mg/dl) (within 3 months); n (%)               | 203 (13.8%) | 452 (16.6%)   | -0.07 | ** (0.4%)     | 32 (0.8%)     | -0.05 | N/A           | N/A           | #VALUE! | 484 (7.3%)   | #VALUE!      | #VALUE! |
| Lab values- BUN (mg/dl) (within 6 months); n (%)               | 290 (19.7%) | 642 (23.1%)   | -0.08 | 18 (0.7%)     | 49 (1.3%)     | -0.06 | N/A           | N/A           | #VALUE! | 308 (7.8%)   | 691 (10.4%)  | -0.09   |
| Lab values- Creatinine (mg/dl); v2; n (%)                      | 297 (20.2%) | 679 (24.4%)   | -0.10 | 20 (0.8%)     | 52 (1.3%)     | -0.05 | N/A           | N/A           | #VALUE! | 317 (8.1%)   | 731 (11.0%)  | -0.10   |
| Lab values- Creatinine (mg/dl) (within 3 months) v2; n (%)     | 206 (14.0%) | 483 (17.4%)   | -0.09 | 12 (0.5%)     | 34 (0.9%)     | -0.05 | N/A           | N/A           | #VALUE! | 218 (5.5%)   | 517 (7.8%)   | -0.09   |
| Lab values- Creatinine (mg/dl) (within 6 months) v2; n (%)     | 297 (20.2%) | 679 (24.4%)   | -0.10 | 20 (0.8%)     | 52 (1.3%)     | -0.05 | N/A           | N/A           | #VALUE! | 317 (8.1%)   | 731 (11.0%)  | -0.10   |
| Lab values- HDL level (mg/dl); n (%)                           | 164 (11.1%) | 376 (13.5%)   | -0.07 | 12 (0.5%)     | 37 (1.0%)     | -0.06 | N/A           | N/A           | #VALUE! | 176 (4.5%)   | 413 (6.2%)   | -0.08   |
| Lab values- HDL level (mg/dl) (within 3 months); n (%)         | 90 (6.1%)   | 211 (7.6%)    | -0.06 | ** (0.3%)     | 23 (0.6%)     | -0.04 | N/A           | N/A           | #VALUE! | 234 (3.5%)   | #VALUE!      | #VALUE! |
| Lab values- HDL level (mg/dl) (within 6 months); n (%)         | 164 (11.1%) | 376 (13.5%)   | -0.07 | 12 (0.5%)     | 37 (1.0%)     | -0.06 | N/A           | N/A           | #VALUE! | 176 (4.5%)   | 413 (6.2%)   | -0.08   |
| Lab values- LDL level (mg/dl); v2; n (%)                       | 167 (11.3%) | 387 (13.9%)   | -0.08 | 13 (0.5%)     | 37 (1.0%)     | -0.06 | N/A           | N/A           | #VALUE! | 180 (4.6%)   | 424 (6.4%)   | -0.08   |

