### 1.4 Required power for primary endpoint and noninferiority margin (if applicable)

Assuming a non-inferiority margin of 1.80, it was determined that 4,094 patients would be needed to achieve 90% power to conclude noninferiority of apixaban over standard therapy at one-sided alpha level of 0.025.

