## 9. Balance Assessment

**Action report links:**

Optum: <https://bwh-dope.aetion.com/projects/details/1484/results/64541/result/0>

Marketscan: <https://bwh-dope.aetion.com/projects/details/1481/results/64542/result/0>

Medicare: <https://bwh-dope.aetion.com/projects/details/1483/results/64543/result/0>

Date conducted: 1/19/2021

After review of initial feasibility and power analyses, complete creation of the remaining covariates from Section 6.2. Again, using the dummy outcome of a 90-day gap in database enrollment, complete a 1:1 PS-matched analysis. The PS should include the complete list of covariates.

- Provide plot of PS distributions stratified by treatment group.

Note- Please refer to **Appendix B**.

- Report covariate balance after matching.

Note- For Table 1, please refer to **Appendix B**.

- Report reasons for censoring by treatment group.

|  | Overall | Referent | Exposure |
|--|---------|----------|----------|
|--|---------|----------|----------|

|                                                                                                                               |                |                |                |
|-------------------------------------------------------------------------------------------------------------------------------|----------------|----------------|----------------|
| Dummy outcome                                                                                                                 | 67 (0.94%)     | 25 (0.70%)     | 42 (1.18%)     |
| Death                                                                                                                         | 103 (1.44%)    | 49 (1.37%)     | 54 (1.51%)     |
| Start of an additional exposure                                                                                               | 232 (3.25%)    | 175 (4.90%)    | 57 (1.60%)     |
| End of index exposure                                                                                                         | 4,701 (65.84%) | 2,202 (61.68%) | 2,499 (70.00%) |
| Specified date reached                                                                                                        | 857 (12.00%)   | 424 (11.88%)   | 433 (12.13%)   |
| End of patient enrollment                                                                                                     | 425 (5.95%)    | 198 (5.55%)    | 227 (6.36%)    |

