| Apixaban (dose of 10 mg twice daily for 7 days, followed by 5 mg twice daily for 6 months) verus conventional therapy (subcutaneous enoxaparin, followed by warfarin)                                                                                                                                                                                                                                                                                                                                |                                                                                                                                                                                                                                                             |                                                                                                                                                                                                                                                                                  | Color coding                                                                                                                                                                                                                                                                                                                                                                                                                                                                                                       |

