| Use of Angiogenesis inhibitors; n (%)                                             | ** (0.1%)           | ** (0.0%)           | 0.04        | ** (0.0%)           | ** (0.1%)           | -0.04         | ** (0.1%)       | ** (0.1%)       | 0.00         | #VALUE!           | #VALUE!           | #VALUE! |         |      |
| Use of Oral Immunosuppressants; n (%)                                             | ** (0.1%)           | ** (0.2%)           | -0.03       | 13 (0.5%)           | ** (0.3%)           | 0.03          | 12 (0.2%)       | ** (0.2%)       | 0.00         | #VALUE!           | #VALUE!           | #VALUE! |         |      |
| Use of fondaparinux or Bivalirudin; n (%)                                         | ** (0.2%)           | ** (0.1%)           | 0.03        | 13 (0.5%)           | ** (0.1%)           | 0.07          | ** (0.2%)       | ** (0.1%)       | 0.03         | #VALUE!           | #VALUE!           | #VALUE! |         |      |
| Use of other direct thrombin inhibitors (lepirudin, desirudin, argatroban); n (%) | 0 (0.0%)            | 0 (0.0%)            | #DIV/0!     | 0 (0.0%)            | #DIV/0!             | 0 (0.0%)      | 0 (0.0%)        | 0 (0.0%)        | #DIV/0!      | 0 (0.0%)          | 0 (0.0%)          | #DIV/0! |         |      |
| Use of Ticagrelor ON CED; n (%)                                                   | 0 (0.0%)            | 0 (0.0%)            | #DIV/0!     | ** (0.0%)           | ** (0.1%)           | -0.04         | ** (0.0%)       | ** (0.1%)       | -0.04        | #VALUE!           | #VALUE!           | #VALUE! |         |      |
| Use of Ticagrelor; n (%)                                                          | 0 (0.0%)            | 0 (0.0%)            | #DIV/0!     | ** (0.0%)           | ** (0.1%)           | -0.04         | ** (0.0%)       | ** (0.3%)       | -0.08        | #VALUE!           | #VALUE!           | #VALUE! |         |      |
| Number of D-dimer tests                                                           |                     |                     |             |                     |                     |               |                 |                 |              |                   |                   |         |         |      |

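### In MarketScan the heparin/LMWH covariate is very probably not captured, so 38.7% of matched pairs are not directly adjusted for it and the pooled balance of 0.00 describes Optum and Medicare almost alone

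*Combined protocol and SAP*

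**What the plan says.** Section 9 plans a 1:1 propensity score match and states: "The PS should include the complete list of covariates". The covariates are those in the Appendix B tables. The Other Medications block there has a row "Use of heparin and other low-molecular weight heparins; n", and further down the same tables is a row "Use of fondaparinux or Bivalirudin; n". Appendix A describes the comparator of the emulated trial as "conventional therapy (subcutaneous enoxaparin, followed by warfarin". In Section 6.1 this study's own comparator is new initiation of warfarin. The trial's limits on heparin, LMWH or fondaparinux treatment before study drug are marked N/A in Appendix A, so no eligibility rule controls such use here.

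The printed heparin/LMWH figures (warfarin vs apixaban, standardized difference) are:

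| | Unmatched | Matched |
|---|---|---|
| Optum | 840/1,472 (57.1%) vs 122/2,783 (4.4%), 1.39 | 95 (19.4%) vs 101 (20.6%) of 490, -0.03 |
| MarketScan | suppressed count (0.1%) of 2,464 vs suppressed count (0.0%) of 3,874, 0.04 | 1 vs 0 of 1,381, 0.04 |
| Medicare | 2,098/4,983 (42.1%) vs 154/3,406 (4.5%), 0.99 | 156 (9.2%) vs 153 (9.0%) of 1,699, 0.01 |
| Pooled | spreadsheet error | 252 (7.1%) vs 254 (7.1%) of 3,570, 0.00 |

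The documents do not comment on the MarketScan figure.

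**The concern.** Two databases show a very large difference between arms on this variable and the third shows almost no use in either arm. If the third figure is a capture failure, the MarketScan propensity score contains a column of near-constant zeros. Its printed balance then carries no information, and the three models that are pooled do not adjust for the same thing.

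Two things are at stake. The first is confounding: if heparin/LMWH around initiation marks patients who differ in recurrence or bleeding risk, more than a third of the matched pairs may carry a difference that nobody can see. The second is the balance review. Section 10 halts the work until the investigators, FDA and advisory board members have looked at balance, and the pooled row tells them that this covariate is perfectly balanced.

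**Working it through.** **1. Reproduce the printed differences.** With SMD = (p1 - p2)/sqrt{[p1(1 - p1) + p2(1 - p2)]/2}, the unmatched rows give 1.391 for Optum (printed 1.39), 0.992 for Medicare (0.99) and 0.045 for MarketScan from the rounded percentages (0.04). The matched rows give -0.031, 0.006 and 0.038 (from 1/1,381 vs 0), and -0.002 pooled. All agree with the tables, so the arithmetic is sound and the question is what went into it.

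**2. How far MarketScan is from the others.** A printed 0.1% of 2,464 means 2 or 3 patients. At the Medicare rate one would expect 0.421 × 2,464 = 1,037, and at the Optum rate 0.571 × 2,464 = 1,407. Small-cell suppression does not explain the gap, because the percentages are printed and the matched table shows the counts 1 and 0.

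**3. Is drug capture in general missing?** No. Among unmatched MarketScan warfarin starters, opioids are recorded in 45.7% and NSAIDs in 14.1%. Fondaparinux/bivalirudin is recorded in 13 (0.5%), more than all heparins and LMWHs together. In Optum and Medicare that same row is 0.2%, against 57.1% and 42.1% for heparin/LMWH.

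**4. Weight of MarketScan in the pooled row.** MarketScan contributes 1,381/3,570 = 38.7% of pairs. Of the 252 pooled warfarin users, 95 + 156 = 251 come from Optum and Medicare; of the 254 pooled apixaban users, 101 + 153 = 254 do.

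**5. Illustration of what the pooled row could hide.** Let w and a be the true use in the MarketScan matched arms. Pooled use is then (251 + 1,381w)/3,570 against (254 + 1,381a)/3,570. The values of w and a are assumptions:

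| Assumed w vs a | MarketScan SMD | Pooled use | Pooled SMD |
|---|---|---|---|
| 10% vs 4.5% | 0.21 | 10.9% vs 8.9% | 0.07 |
| 20% vs 4.4% | 0.49 | 14.8% vs 8.8% | 0.19 |
| 42.1% vs 4.5% (Medicare, unmatched) | 0.99 | 23.3% vs 8.9% | 0.40 |
| 57.1% vs 4.4% (Optum, unmatched) | 1.39 | 29.1% vs 8.8% | 0.54 |

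**6. Power.** The plan's figures reproduce with Phi{sqrt(D/4) × ln(1.8/0.84) - 1.96}: D = 98.1 gives 0.965. In 1:1 matching the yield is limited by the smaller arm. The smaller-arm retention is 490/1,472 = 33.3% in Optum (warfarin), 1,699/3,406 = 49.9% in Medicare (apixaban) and 1,381/2,464 = 56.0% in MarketScan (warfarin). Suppose a working variable lowered the MarketScan yield:

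- At 33.3%, about 820 pairs remain. D = 12.67 + 49.81 + 1,640 × 0.01313 = 84.0, and power is about 0.94.
- At 49.9%, about 1,229 pairs remain. D = 12.67 + 49.81 + 2,458 × 0.01313 = 94.8, and power is about 0.96.
- With MarketScan left out altogether, D is about 62 and power about 0.85.

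**The case against.** **The cause is not documented.** Code lists sit in an external folder, and a drug-list error, a mapping error and a limit of the data feed are all possible. MarketScan warfarin starters were also more often in hospital in the prior 30 days (94.4%, against 82.7% in Optum and 72.3% in Medicare), so more of their heparin may have been given where it is not recorded. That could lower the figure, but it hardly explains 2 or 3 patients in 2,464. Non-capture remains an inference, though a strong one.

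**A reader might infer a hidden imbalance of 0.99 to 1.39 in MarketScan.** The documents do not support this. Those are unmatched values from other databases, and matching in MarketScan did act on plausible correlates: hospital days went from 0.32 to 0.03, hospitalization in the prior 30 days from 0.33 to -0.05, PT/aPTT tests from 0.17 to 0.02 and INR tests from 0.23 to 0.12. Only direct adjustment is known to be missing.

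**A reader might infer that the missing variable inflated the MarketScan match yield and so the power.** Comparing retained warfarin starters (33.3%, 34.1%, 56.0%) suggests it, but apixaban is the smaller arm in Medicare. On the smaller-arm basis Medicare, where the variable works, is at 49.9% and not far from MarketScan's 56.0%. The inference does not stand.

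**If heparin/LMWH is part of the comparator strategy, not matching on it is no bias.** This is right as far as it goes, and it is why the role of the variable must be settled first. But no single role justifies matching on it in two databases and not in the third. Matching has already cut use among retained warfarin patients to 19.4% in Optum and 9.2% in Medicare.

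**The propensity scores differ by database anyway, and the per-database cells are visible.** Laboratory values are N/A for Medicare and race appears only for Medicare. Those gaps are visible as such, whereas the MarketScan heparin cells look like a measured near-zero and enter the pooled row as data.

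**Conclusion.** The concern holds in a limited form. It is very probable that heparin/LMWH use is not captured in MarketScan, and it follows that 1,381 of 3,570 pairs are not directly adjusted for the clinical covariate with the largest pre-matching difference in the other two databases. The pooled 0.00 should not be read as evidence of balance in the full matched set.

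The size and direction of any bias in the hazard ratio are unknown. The pooled standardized differences of 0.07 to 0.54 illustrate assumed rates and are not estimates; the upper end also assumes that matching on other covariates did nothing. The effect on power is minor: 0.94 to 0.96 against the stated 0.965, still above the 90% that Section 1.4 gives for the trial. What matters is comparable adjustment across databases and an accurate balance table. Section 13 records no comparative result yet, so this can be settled without knowledge of the outcome comparison.

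**What to change.** Before the comparative analysis:

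1. State whether heparin/LMWH around initiation is a confounder to match on or part of the comparator strategy, and treat it the same way in all three propensity score models.
2. If it stays in the propensity score, trace the cause in MarketScan (drug list, mapping or data feed), repair the variable if possible and check that its prevalence is plausible. Then rerun the MarketScan match and reissue the balance table and the Section 10 power.
3. If it cannot be repaired, mark the MarketScan cells as not measured and take them out of the pooled balance row. Then either drop the variable from all three models or report the pooled estimate with and without MarketScan.

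The cost is one variable check, some rematching and new tables, and possibly a smaller MarketScan matched set. Dropping the variable everywhere would mean rematching all three databases. The estimate without MarketScan would have power of about 0.85.
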